6 STATISTICAL CONSIDERATIONS

6.1 Primary Endpoint

The primary outcome of interest will include the following endpoint:

- Scores of HRQOL obtained from the PedsQL™ scales

The secondary outcomes of interest will include the following:

- Scores of difficulty with events faced by parents of children with serious illness from the PIP-D
- Scores for patient sleep behavior from the SDSC DIMS
- Incidence and sources of parental financial distress following patient's AML/MDS diagnosis
- Incidence of sibling behavior change following patient's AML/MDS diagnosis
- Financial toxicity scores obtained from the financial toxicity survey

6.2 Control of Bias and Confounding

This is an observational cohort study, so subjects are not assigned by a process of randomization and are therefore subject to bias. However, analyses of our data will control for potential confounding by various patient- and hospital- level factors. Additionally there is a possibility of exposure misclassification given that patients who are discharged more than 3 days after chemotherapy completion but well before neutropenia recovery will still be included in the inpatient management group. To account for this imperfect specificity, sensitivity analyses will be performed utilizing a less strict threshold for discharge classification (e.g., 5 or 10 days post-chemotherapy).

6.3 Statistical Methods

6.3.1 Analysis of Primary Outcomes of Interest

Propensity score analyses will be used to adjust for potential confounding by baseline covariates. First, bivariate analyses will be performed to evaluate relationships between each baseline covariate and neutropenia management strategy as well as each outcome of interest. Next, propensity scores will be derived from the predicted probabilities estimated from logistic regression models of the use of outpatient versus inpatient management during neutropenia conditional on all baseline factors determined to be true confounders (i.e., those associated with both exposure and outcome) and those determined to be potential confounders (i.e., those associated only with the outcome interests). Patients will then be stratified into five groups using quintiles of the estimated propensity score. The distributions of exposure within the quintiles will be examined for sufficient sample sizes and balance. Within each stratum, the patients managed as outpatient and those managed as inpatient will ideally have similar values of the propensity score and likewise the distribution of measured baseline covariates will be comparable between them.

PedsQL™ items will be reverse scored and linearly transformed to a scale of 0 to 100 such that higher scores will be reflective of better HRQOL. The PedsQL™ total score will be calculated as the sum of the item-specific scores divided by the number of answered items (33, 34).

We will utilize linear mixed effect models to test the association between neutropenia management strategy and the PedsQL™ total score. Specifically, the two repeated measures of the PedsQL™ total score will be the outcome and regressed on time, group (outpatient versus inpatient) and interaction between time and group will be the fixed effects, and a subject level random effect will be included to account for the potential correlations between the repeated measures. Such mixed models are more powerful than ANCOVA or analysis of change scores, and they benefit from the added power arising from any correlation of repeated measures over time. A significant group by time interaction will suggest that the change of PedsQL™ is different between the two groups. Adjustment for differences in covariates across neutropenia management groups will be accomplished through the propensity score outlined above, and by controlling for confounding of any remaining unbalanced potential confounders. Secondary analyses will be performed for the cancer and fatigue modules as well as for the physical and psychosocial subscales of the PedsQL™.

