3.3 Total Number of Study Sites/Total Number of Subjects Projected

3.3.1 Duration of Study Participation

Eligible patients will be approached for consent at any time from initial AML or MDS diagnosis through the last day of chemotherapy in the frontline treatment course under study. The maximum duration of enrollment is from the initiation of their current chemotherapy course until the last day of their subsequent chemotherapy course. This duration is estimated to be approximately 30-40 days.

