6.4 Sample Size and Power

We expect to prospectively identify approximately 139 patients and assuming 90% of identified patients will be discharge eligible and 85% will consent, the anticipated study population will be 118 patients and their caregivers. Approximately 40% will be managed as outpatients, so we expect 47 outpatients and 71 inpatients. The power calculation was conducted under the framework of a multivariate general linear hypothesis for general linear models, using the Wilks Lambda test with a significance level of 0.05 (35, 36). Assuming a standard deviation (SD) of 20 for the PedsQL™ total score, if there is no correlation we will have 80% power to detect a large effect size of 0.75 that is a 15.0 point difference in the mean change scores between the two groups. If the correlation is as high as 0.8 we will have 80% power to detect a small effect size of 0.34, that is a 6.8 point difference in the mean change scores between the two groups.

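### Propensity covariates are admitted only on an observed association with the outcome in about 118 patients, with no cut-off and no forced-in set, so real confounders can drop out by chance

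*Combined protocol and SAP*

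**What the plan says.** Section 6.3.1 begins with a screen: "bivariate analyses will be performed to evaluate relationships between each baseline covariate and neutropenia management strategy as well as each outcome of interest". The propensity model for outpatient versus inpatient management is then fitted "conditional on all baseline factors determined to be true confounders (i.e., those associated with both exposure and outcome". The sentence goes on to open a second route into the model, which needs no link with the management strategy: "and those determined to be potential confounders (i.e., those associated only with the outcome interests". Patients are grouped by quintile of the score. Later in the same section, covariate differences are handled through the score and "by controlling for confounding of any remaining unbalanced potential confounders".

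The plan gives no p-value or effect-size cut-off for the screen and names no covariate that is always included. It does not say whether the PedsQL association is judged on the baseline score, the follow-up score or the change, or whether one score serves all outcomes.

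On size, Section 6.4 states that "the anticipated study population will be 118 patients and their caregivers". It divides that total between the two groups as follows: "Approximately 40% will be managed as outpatients, so we expect 47 outpatients and 71 inpatients". Section 6.2 accepts that the comparison is not randomised and relies on covariate control.

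**The concern.** The two clauses of the rule differ only on the exposure association. Both require an outcome association, so the outcome screen alone decides whether a covariate is kept. This has two consequences.

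First, the adjustment is built from the outcome data it will be used to analyse. With no cut-off, the choice of covariates can be made after the outcomes are known, and intervals computed as if the score had been fixed ignore that step.

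Second, whether a covariate confounds does not depend on its p-value in a sample of this size. Course number is a plausible example. Families may be approached "at any time from initial AML or MDS diagnosis through the last day of chemotherapy" of the course under study, so patients will differ in how far through treatment they are. Course number is already abstracted under Section 5.1.2, yet it would be adjusted for only if it passed the screen.

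Because measured-covariate adjustment is the main defence against confounding here, a rule that loses confounders at random weakens the comparison where it most needs protection.

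**Working it through.** **1. The plan's own figure.** Inputs from Section 6.4: 47 and 71 patients, SD 20, and "using the Wilks Lambda test with a significance level of 0.05" (taken as two-sided). The SD of change is 20 × √(2(1 − ρ)), which is 28.28 at ρ = 0 and 12.65 at ρ = 0.8. The standard error multiplier is √(1/47 + 1/71) = 0.188.

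- ρ = 0: 15.0 / (28.28 × 0.188) = 2.82, power 80.5% (normal) or 79.9% (t).
- ρ = 0.8: 6.8 / (12.65 × 0.188) = 2.86, power 81.6% or 80.9%.

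The stated 80% power reproduces. It concerns the primary test. The plan gives no figure for the screening step.

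**2. Chance that the screen misses a confounder.** For a true correlation r with a single outcome, the Fisher-z statistic has mean atanh(r) × √(n − 3). With n = 118, √115 = 10.72. The miss probability is the chance of staying inside ±z. The cut-off is an assumption, so two are shown.

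| r | mean of z | missed at p<0.05 (z = 1.960) | missed at p<0.20 (z = 1.282) |
|---|---|---|---|
| 0.10 | 1.08 | 81% | 57% |
| 0.15 | 1.62 | 63% | 37% |
| 0.20 | 2.17 | 42% | 19% |
| 0.25 | 2.74 | 22% | 7% |
| 0.30 | 3.32 | 9% | 2% |

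The 50% point lies at r = 0.18 for p<0.05 and r = 0.12 for p<0.20.

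Sample size moves these figures a little. The 118 equals 139 × 0.85. Applying the 90% eligibility rate in Section 6.4 as well gives 139 × 0.90 × 0.85 = 106, where the misses at p<0.05 for r = 0.15 and 0.20 are 66.5% and 46.1%. Child self-report covers only ages 5 and over. At an assumed n of 80, the miss at r = 0.20 is 57%.

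**3. If an association with any outcome is enough.** With six outcomes, the same r with each and residual correlation 0.4 (all assumed), the misses at p<0.05 fall to 22% at r = 0.15 and 7% at r = 0.20.

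**4. Illustration of bias.** Assumptions: n = 118, eight confounders each with outcome correlation 0.18 and exposure log-odds 0.35, all acting in the same direction, no true effect, adjustment by propensity quintile only.

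| Covariates in the score | Bias (SD) | False positives |
|---|---|---|
| All eight | 0.03 | about 5% |
| Screened at p<0.20 | 0.08 | 7% |
| Screened at p<0.05 | 0.16 | 14% |

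Variants at p<0.05:

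- Four confounders instead of eight: 0.09 SD and 6%.
- Eight confounders with random directions: mean bias 0.00, false positives 4.4%, and mean absolute error 0.153 SD against 0.151 SD for the full set.

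**5. The further adjustment in Section 6.3.1.** Same eight-confounder setting, screened at p<0.05:

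- Only covariates that passed the outcome screen qualify: no change (0.16 SD, 14%).
- Any measured covariate still unbalanced by more than 0.25 SD qualifies: 0.06 to 0.07 SD, 5 to 6%.
- The same with a 0.1 SD limit: 0.04 SD, 4.9%.

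**The case against.** Several points on the other side stand.

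- **The rule is not a double test.** A reader who stops at the first clause may infer that a covariate must be associated with both exposure and outcome. The second clause keeps those associated with the outcome alone. Favouring outcome-related covariates is sound in principle; the weakness is judging this by bivariate results in the study's own small sample.
- **Losing confounders more often than not.** This is tempting to infer, but holds only for r below about 0.18 at an assumed p<0.05 with one outcome. It fails at r = 0.20, at p<0.20 once r exceeds about 0.12, and if any of several outcomes can qualify a covariate. The plan does not even say that the screen is a significance test.
- **The bias figure.** It needs confounders that push the same way, which nothing in the documents establishes.
- **Conversion to PedsQL points.** One might multiply 0.16 SD by the change-score SDs. The primary test is the group-by-time interaction, and the listed fixed effects include no propensity-by-time term. If quintiles enter only as main effects and all pairs are complete, the interaction estimate is the same whichever covariates are chosen. The selection rule acts directly on the quintile-adjusted models of Section 6.3.2, and on the primary test only if the score is allowed to act on change.
- **A different score for each outcome.** The wording permits this but does not say it.
- **Course number.** The documents show variable entry time. They do not show that course number affects discharge practice or quality of life.

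The strongest defence is the further adjustment for unbalanced covariates, which could recover most of the loss. It rests on the term potential confounders, which the same section defines by outcome association. Read that way, it recovers nothing the screen dropped.

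**Conclusion.** The concern holds in a limited form. Section 6.3.1 makes entry to the propensity model depend on the observed outcome association, with no cut-off and no forced-in set. At n = 118 with one outcome, a confounder with correlation 0.15 to 0.20 is missed about 63% to 42% of the time if p<0.05 is used, and 37% to 19% if p<0.20 is used. The cut-offs and correlations are assumptions, because the plan supplies neither.

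The 0.16 SD and 14% describe one adverse scenario without the further adjustment; they are not a prediction for this study. How much confounding survives turns on how an undefined step is read, which is itself a reason to amend. The documents do not support saying that the results will be biased, or by how many points. The change should be made because it is cheap and removes both the dependence on outcome data and the chance loss of a named confounder.

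**What to change.** Replace the selection rule in Section 6.3.1 with a covariate list fixed before outcome data are seen, drawn from Section 5.1.2 and the Visit 1 surveys. Candidates are age, course number, regimen, risk group, clinical status at chemotherapy completion (such as mucositis and nutritional status) and socioeconomic factors (such as insurance, income and caregiver marital status). Use only values known by chemotherapy completion, and keep the list modest because only about 47 outpatients are expected.

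Use one propensity score for all outcomes. Keep the bivariate tables as description only. Let the further adjustment apply to any listed covariate that stays unbalanced after stratification, by a stated measure and limit, whatever its association with the outcome.

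The cost is SAP wording, with no new data. The downside is a slight loss of precision from uninformative covariates: in simulation, adding seven pure-noise covariates raised the standard error from 0.184 to 0.196 (0.196 / 0.184 = 1.07, about 7%).

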2.1 Objectives

The primary objective of this study is to compare patient and caregiver reported quality of life and other PCO (established through previous qualitative interviews conducted by a medical sociologist at CHOP) for inpatient versus outpatient management of neutropenia in children with AML or MDS receiving standard intensive AML frontline chemotherapy.

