Visit 2 will occur within the period after absolute neutrophil count recovery and ideally prior to the start of the subsequent course of chemotherapy, but no later than the last day of chemotherapy in that next treatment course. For the small number of patients who will begin the next course of chemotherapy before count recovery, Visit 2 will occur within the period from one day prior to the start of chemotherapy in that next treatment course and no later than the last day of chemotherapy in that course. This visit will include:

- 3 follow-up health-related quality of life (HRQOL) PedsQL™ surveys (core, cancer, and fatigue)
- 1 PCO survey
- 1 Financial toxicity survey

All surveys will be administered via paper or a smart device and will last a total of 15-30 minutes per respondent. In the case that the child is 5 years of age or older, the PedsQL child self-report and parent proxy-report scales will be administered to the child and caregiver, respectively. If the child is between 5 and 8 years of age, Study Personnel will read the survey questions to the patient. There is an illustrated response aid for these young patients. These age-specific PedsQL instruments have been previously validated. The child will indicate their answer as 'Not at all', 'Sometimes', or 'A lot' by pointing to a smiling, middle, or frowning face, respectively. If the child is under 5 years of age, only the parent-proxy version will be administered. Caregivers will also be asked to complete the PCO

survey at follow-up. The PCO survey assesses dimensions such as parental stress and anxiety, patient's sleep behaviors, impact on siblings, and hospital discharge teaching practices. In addition, caregivers will be asked to complete the financial toxicity survey again at follow-up. The caregiver completing the follow-up assessments must be the same caregiver who completed the baseline assessments. We will provide a \$50 gift card to each child-parent dyad upon completion of the PCO survey, financial toxicity survey, and follow-up quality of life surveys. If the child and caregiver do not complete both visits, they will only be compensated a portion of the \$50 for the visits they do complete.

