The format, instructions, response scale and scoring methods for the three PedsQL scales are identical. Each is available in parallel child self-report and parent proxy-report formats. Child self-report versions include ages 5-7 years, 8-12 years and 13-18 years. Parent proxy report versions include ages 1-2 years, 2-4 years, 5-7 years, 8-12 years and 13-18 years. In this study we will administer the Child Self-Report versions of the scales for children 5 years of age and older in addition to the Parent Proxy-Report versions.

A 5-point Likert response scale is used across child self-report for ages 8-18 and parent proxy-report (anchored by 0 = never a problem to 4 = almost always a problem). Responses to each question are used to assemble a score.

Each of these scales demonstrates internal reliability acceptable for group comparisons (PedsQL™ Generic Core Total Scale Score [Cronbach's α = 0.88 child, 0.93 parent report]; Multidimensional Fatigue Total Scale Score [α = 0.89 child, 0.92 parent report]; most Cancer Module Scales [average α = 0.72 child, 0.87 parent report]) (29). These scales have also been shown to be sensitive to change over time in children with cancer (30).

- **PCO Survey**
 - Pediatric Inventory for Parents-Difficulty scales (PIP-D)-(42 items)
 - Parental stress and anxiety (9 items)
 - Sleep Disturbance Scale for Children (SDSC): Disorders of Initiating and Maintaining Sleep domain (DIMS) (7 items)
 - Impact on Siblings (7 items)
 - Hospital Discharge Teaching Practices (4 items)

The PCO survey will be completed by the parent during study Visit 2. The PCO includes established measures of parental stress (PIP-D) and sleep disturbance in children (SDSC DIMS) as well as survey questions designed to measure the incidence and sources of parental financial stress; sources of parenting, emotional, domestic and financial support; the incidence and nature of sibling behavioral change, and the receipt of training prior to discharge from the hospital.

The PIP-D assesses stress-related difficulty with events faced by parents of children with serious illness across four domains: communication (e.g., with child, partner, or health care team), emotional functioning (e.g., impact of illness on sleeping and mood), child's medical care (e.g., carrying out medical regimen), and role functioning (e.g., impact of illness on

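### The primary PedsQL total score is not tied to a respondent, and the stated 80% power cannot hold for child self-report unless almost no enrolled child is under 5

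*Combined protocol and SAP*

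**What the plan says.** Section 2.1 sets out to "compare patient and caregiver reported quality of life and other PCO". Section 6.1 gives the primary endpoint as "Scores of HRQOL obtained from the PedsQL™ scales". Section 6.3.1 tests the "association between neutropenia management strategy and the PedsQL™ total score". In its primary model, "the two repeated measures of the PedsQL™ total score will be the outcome", with time, group and their interaction as fixed effects. For correlation, "a subject level random effect will be included to account for the potential correlations between the repeated measures". The same section makes the cancer and fatigue modules secondary, so the primary instrument is in effect the Generic Core total score.

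On respondents, section 5.1.3 says of the PedsQL scales: "Each is available in parallel child self-report and parent proxy-report formats". Sections 4.3 and 4.4 have both forms completed at each visit when the child is 5 or older. For younger children: "If the child is under 5 years of age, only the parent-proxy version will be administered". Section 3.4.1.1 sets an upper age limit (under 19 at diagnosis) but no lower one.

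In section 6.4, "the anticipated study population will be 118 patients and their caregivers", split 47 outpatient and 71 inpatient. With an SD of 20 and a 0.05 level, it claims 80% power for a 15.0-point difference in mean change at correlation 0, or 6.8 points at correlation 0.8. Neither the endpoint, the scoring rule, the model nor the power statement names a respondent.

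**The concern.** A dyad with a child of 5 or older yields two Generic Core total scores per visit, and the plan does not say which one the primary model uses. Four analyses fit the text:

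- proxy report only;
- self-report only;
- both, tested separately;
- a mixed score, with self-report where it exists and proxy otherwise.

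They differ in sample size, in error rate and in what is being estimated. The single power figure cannot describe all of them. If both reports are tested at 0.05, no multiplicity rule protects the primary conclusion. If both enter one model, the only random effect is at subject level and there is no term for reporter. The comparison is non-randomised and unblinded, so an open choice of respondent could be made after both results are known.

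**Working it through.** **1. Reproduce the stated power.** Inputs from section 6.4: 47 and 71 patients, SD 20 at each visit, level 0.05 (taken as two-sided), correlation ρ = 0 or 0.8. With two groups and two visits, the group-by-time test is a two-sample test on change scores:

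- SD of change = 20 × √(2(1 − ρ)), which is 28.28 at ρ = 0 and 12.65 at ρ = 0.8.
- Standard error of the difference = SD of change × √(1/47 + 1/71), which is 5.319 and 2.379.
- Noncentrality = difference / standard error: 15.0/5.319 = 2.820 and 6.8/2.379 = 2.859.
- Noncentral t on 116 df: power 79.9% and 80.9%.

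The stated 80% is therefore correct for 118 pairs of scores. A one-sided test (88.0% and 88.8%, normal approximation) does not match it. Nor does using SD 20 without conversion to change scores (97.9% and 44.0%).

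**2. Apply the same calculation to child self-report.** Children under 5 contribute no self-report. Their share is not in the documents, so it is an assumption here. N = 118 × (1 − share), with the split kept at about 40:60.

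| Assumed share under 5 | N (out / in) | Power, 15.0 points, ρ = 0 | Power, 6.8 points, ρ = 0.8 | 80%-power difference, ρ = 0 / 0.8 |
|---|---|---|---|---|
| 10% | 106 (42 / 64) | 75.4% | 76.5% | 15.9 / 7.1 |
| 20% | 94 (38 / 56) | 70.4% | 71.6% | 16.8 / 7.5 |
| 30% | 83 (33 / 50) | 64.7% | 65.9% | 18.0 / 8.0 |
| 40% | 71 (28 / 43) | 57.7% | 58.8% | 19.5 / 8.7 |
| 50% | 59 (24 / 35) | 50.3% | 51.4% | 21.4 / 9.6 |

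Power drops below 78% at N = 112 for ρ = 0 (6/118, about 5% under 5) and at N = 109 for ρ = 0.8 (9/118, about 8%).

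**3. Error rate if both reports are tested as primary.** For two two-sided tests at 0.05 whose statistics are bivariate normal with correlation r, familywise error = 1 − P(|Z₁| < 1.96 and |Z₂| < 1.96). This gives 8.3% at r = 0.7 and 9.5% at r = 0.3. The independence ceiling is 1 − 0.95² = 9.75%. The documents give no value for r, so 0.3-0.7 is an assumption.

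**4. Check the starting N.** Section 6.4 applies 90% discharge-eligible and 85% consent to 139 identified patients: 139 × 0.90 × 0.85 = 106.3. The figure of 118 follows from consent alone (139 × 0.85 = 118.2). At N = 106, power is 75.4% and 76.5% before any child is lost for age. The proxy forms listed in section 5.1.3 also start at age 1, while eligibility has no lower limit, so even proxy report may not cover every patient.

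**The case against.** Section 6.4 never says that its power refers to self-report. For one score pair per patient the arithmetic is right. That stands: the fault is an unnamed respondent, and the loss of power is conditional on self-report being the primary score.

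Several stronger readings are tempting, and the documents do not support them:

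- **Only proxy report can supply 118.** A mixed score also gives one value per patient, so the sample size does not reveal which respondent was intended.
- **Most dyads yield two scores.** No age distribution is given, so neither that nor any particular loss of power can be stated as fact.
- **Six primary tests, three scales by two respondents.** Section 6.1 is loosely worded, but section 6.3.1 makes the cancer and fatigue modules secondary.
- **Both reports will be co-primary, with either counting as success.** The plan does not say so. The error rate above applies only if the analysis is run that way.
- **A mixed score would bias the group comparison through age.** The test is on change, and the same caregiver must complete both visits (section 4.4), so the respondent is generally constant within a child. Bias would need age to differ between groups. Age is abstracted and can enter the propensity model, though only if it is associated with outcome. What remains is mainly a difficulty of interpretation.

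It can also be said that this is an observational study. But the plan names a primary outcome, a 0.05 level and a significant interaction as its criterion, so the respondent still has to be fixed in advance.

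**Conclusion.** The concern holds in limited form. No section ties the primary Generic Core total score to a respondent, although the objective covers both. The stated power is right for 118 pairs of scores but cannot carry over to the patient-reported half of the objective unless almost no enrolled child is under 5.

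The direction of the loss is certain if any enrolled child is under 5. Its size rests on the assumed 20-50% under 5, together with the plan's own SD, split and correlations. A reader might infer that section 6.4 is miscalculated, or that 15.0 and 6.8 points are secure for proxy report. Neither follows: the power calculation reproduces, but 118 does not follow from that section's own percentages, and proxy coverage below age 1 is unsettled. This should be corrected before analysis.

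**What to change.** - **Sections 6.1 and 6.3.1:** name one respondent for the primary Generic Core total score and rank the other as key secondary. If both are to be primary, state the multiplicity rule. Parent-proxy report is one reasonable choice because it covers nearly all ages, but it makes the child's own report secondary. That is a substantive decision for the sponsor, given the objective.
- **Section 6.1:** align it with section 6.3.1, so that the cancer and fatigue modules are plainly secondary.
- **Section 6.4:** reconcile the total (106 or 118), state the expected age mix, and say whether children under 1 have a usable proxy form. Then give N and the detectable difference separately for proxy and self-report. Do not simply relabel 15.0 and 6.8 as proxy figures.

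The cost is protocol and SAP text, with no new data or visits. The downside is that less favourable detectable differences will be on record, especially for self-report.

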6.3.2 Analysis of Secondary Outcomes of Interest

Responses to each of the items on the PIP-D were summed to obtain a total score reflecting the amount of difficulty experienced when handling events faced by parents of children with serious illness. Higher scores indicate greater difficulty and increased pediatric parenting stress (31).

Responses to each of the items on the SDSC DIMS subscale are summed to get a total domain score that is mapped to a corresponding T-score using the SDSC scoring sheet. Higher T-scores are reflective of greater clinical severity of symptoms and a T-score greater than 70 is considered pathological (32). For the PCO, we will utilize appropriate standard statistical methods to evaluate the relationships with neutropenia management strategy

(outpatient versus inpatient). For binary outcomes, log-binomial regression with robust error estimates will be employed to obtain risk ratios (95% CI). For continuous outcomes, generalized linear models will be used incorporating the appropriate distribution based on a graphical assessment of the outcome data. All models will be adjusted for baseline propensity scores by quintiles. Log-binomial regression with robust error estimates will also be employed to obtain risk ratios (95% CI) comparing the incidence of any financial toxicity (versus none), separately for each item on the financial toxicity survey as well as overall across all survey items. For the total score obtained from the financial toxicity survey, we will utilize methods comparable to those described for the PedsQL™ total score in section 6.3.1 above.

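### The two-visit mixed model does not have the power advantage section 6.3.1 claims, and the section does not say whether the propensity quintiles interact with time, which decides whether the primary test is adjusted

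*Combined protocol and SAP*

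**What the plan says.** Section 6.3.1 takes the PedsQL total at both visits as the outcome, with fixed effects for time, group and their interaction and a random effect per subject. The interaction carries the inference: "A significant group by time interaction will suggest that the change of" PedsQL differs between the groups. The model is preferred because "Such mixed models are more powerful than ANCOVA or analysis of change scores", and because "they benefit from the added power arising from any correlation of repeated measures over time".

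On confounding, section 6.2 acknowledges that "subjects are not assigned by a process of randomization and are therefore subject to bias". Section 6.3.1 forms the strata ("Patients will then be stratified into five groups using quintiles of the estimated propensity score") and then says "Adjustment for differences in covariates across neutropenia management groups will be accomplished through the propensity score outlined above", plus control for any covariates still unbalanced. It does not say whether the quintiles enter as main effects, interact with time, or define separate within-stratum comparisons. For the secondary outcomes, section 6.3.2 says "All models will be adjusted for baseline propensity scores by quintiles", and it sends the financial toxicity total score back to the methods of 6.3.1.

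Section 6.4 powers the study on the same quantity as the interaction: a "15.0 point difference in the mean change scores between the two groups" at correlation 0, and 6.8 points at correlation 0.8.

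**The concern.** With one baseline and one follow-up per child, a random-intercept model has no information on change beyond the within-child difference, except from children seen once. A claim that it beats change scores therefore looks wrong. A claim that it beats ANCOVA looks reversed when baselines are similar. This is the only comparative reason given for the primary model.

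The second issue follows from the same algebra. Anything in the model that is constant over time cancels from the within-child difference. Quintile main effects are constant over time. An analyst could add them, report a propensity-adjusted result, and leave the tested coefficient untouched. In a non-randomised cohort, the primary conclusion would then be unprotected against any covariate that predicts change in PedsQL.

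**Working it through.** **Inputs.** From section 6.4: 47 outpatients, 71 inpatients, SD 20 at each visit, alpha 0.05 (taken as two-sided), 80% power, correlation r of 0 and 0.8. The values r = 0.3 and 0.5 are added for illustration. The method is noncentral t.

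**1. Reproduce the plan's figures.** The SD of change is 20 × √(2(1 − r)).
- r = 0: SD 28.28, detectable difference 15.03 (plan: 15.0).
- r = 0.8: SD 12.65, detectable difference 6.72 (plan: 6.8, at which power is 80.9%).

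Section 6.4 is therefore a correct calculation for an unadjusted change-score test with 116 df.

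**2. Compare with ANCOVA, similar Visit 1 means.** The residual SD is 20 × √(1 − r²), with 115 df. The variance ratio, ANCOVA to change, is (1 − r²)/(2(1 − r)) = (1 + r)/2, whatever the sample size.

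| r | Interaction / change score | ANCOVA | Variance ratio |
|---|---|---|---|
| 0 | 15.03 | 10.63 | 0.50 |
| 0.3 | 12.57 | 10.14 | 0.65 |
| 0.5 | 10.62 | 9.20 | 0.75 |
| 0.8 | 6.72 | 6.38 | 0.90 |

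A Visit 1 gap of d SDs inflates the ANCOVA variance. With k = 1/47 + 1/71 = 0.03536, the two are equal when (1 − r²)(k + d²/116) = 2(1 − r)k, so d² = 116k(1 − r)/(1 + r). This gives d = 1.17 at r = 0.5 and d = 0.68 at r = 0.8. Beyond that gap the ordering reverses.

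**3. When the model differs from change scores.**
- *Zero variance estimate.* In 20,000 simulated datasets per value of r, the random-intercept variance was estimated at zero in 50% at r = 0 (SE there about 3% smaller), 14% at r = 0.1, 0.1% at r = 0.3 and none at r = 0.5.
- *Children with Visit 1 only.* If a fraction f completes Visit 2, the variance falls relative to complete-case change scores by (1 − r)(1 − f)/2. The documents give no Visit 2 dropout rate. At an assumed 15% missing the gain is 0.2 × 0.15/2 = 1.5% (r = 0.8) to 1 × 0.15/2 = 7.5% (r = 0). At an assumed 30% it is 3% to 15%. Even then the variance is 1.08 to 1.85 times that of complete-case ANCOVA with similar baselines, for 15 to 30% missing.

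**4. How the quintiles enter.** One simulated complete dataset (118 children, r = 0.5), estimate (SE):

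| Quintiles | Mixed-model interaction | Change-score regression |
|---|---|---|
| None | 4.487 (4.012) | 4.487 (4.012) |
| Main effects | 4.487 (4.012) | no counterpart |
| By time | 2.127 (4.312) | 2.127 (4.312), quintile as covariate |

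Main effects change nothing; quintile by time reproduces the quintile-adjusted change score. Missing data do not rescue main effects. With 21 of 139 children lacking Visit 2 (150 fits, r = 0.5), main effects moved the interaction by 0.1 point on average and quintile by time moved it by 4.1.

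**5. Size under assumed confounding.** There is no true effect, a covariate predicts 5 points of change per SD, and 6,000 complete datasets were simulated per scenario. The covariate gap and slope are assumptions, not figures from the documents.

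| Covariate gap | Main effects: bias; rejection at r = 0.5, 0.8 | Quintile by time: bias; rejection |
|---|---|---|
| 0.47 SD | 2.3–2.4 points; 9%, 15% | 0.2 points; 5% |
| 0.83 SD | 4.1 points; 19%, 37% | 0.4 points; 5% |

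**6. Precision cost.** At r = 0.5 the simulated SE rises from 3.88 to 3.94 (1.5%, gap 0.47 SD), from 3.86 to 4.20 (9%, gap 0.83 SD), or from 3.76 to 4.18 (11%) if the covariate does not predict change. Assuming the same ratios at other r (112 df), the detectable differences become 15.3 to 16.7 points at r = 0 and 6.8 to 7.5 at r = 0.8.

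**The case against.** The clause on power is only a rationale. The sample size does not rest on it, the section 6.4 figures are right for the test they describe, and difference in change is a legitimate target that 6.3.1 and 6.4 name consistently. That stands: taken alone, striking the clause is editorial. The further remark that correlation between visits adds power is true and should stay.

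The plan is silent on the form of adjustment rather than wrong. Section 6.3.1 speaks of stratifying patients and of comparability within each stratum. Read as within-stratum comparison, that already gives each quintile its own time effect. This also stands. A reader might infer that the plan commits to main effects and that its primary result will be unadjusted; the documents do not say so. But main effects are a natural reading of adjusting through the score, and the quintile wording in 6.3.2 does not exclude them. An ambiguity that decides whether the primary test is adjusted needs to be closed.

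The bias figures depend on assumed confounding and are zero if no covariate predicts change. They show possible size, not a forecast.

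A reader might also conclude that ANCOVA should replace the primary model. The documents do not support that. Without randomisation the two analyses have different estimands when Visit 1 means differ, and the precision ranking holds only for similar baselines. The largest contrast, 15.0 against 10.6, needs r = 0; at r = 0.8 it nearly vanishes.

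**Conclusion.** The concern holds in two parts. First, the comparative power statement is wrong for the model written. With complete pairs and a positive random-intercept variance there is no gain over change scores. With Visit 1-only children the variance gain is 1.5 to 15%, for r from 0.8 to 0 and an assumed 15 to 30% missing. Against ANCOVA with similar baselines the model is less precise, by a variance factor of 2.0 at r = 0 and 1.11 at r = 0.8.

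Second, and of more consequence, the role of the propensity quintiles in the primary model is unspecified. Under the main-effects reading the tested coefficient is unadjusted. The possible bias and excess false positives in the working are conditional on that reading and on the assumed confounding. A reader might infer that the study is underpowered or its sample size wrong because of the clause; nothing in section 6.4 depends on it. The 15.0 and 6.8 points do, however, describe an unadjusted test. The plan should be amended, but the primary model can stay.

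**What to change.** 1. In section 6.3.1, strike the claim of greater power than ANCOVA or change scores and keep the remark on correlation. Justify the model by its estimand: the difference between groups in change from Visit 1 to Visit 2.
2. State that the propensity quintiles, and any covariate still unbalanced, enter the primary model with an interaction with time. Say the same for the financial toxicity total score in section 6.3.2.
3. Prespecify a sensitivity regression of Visit 2 PedsQL total on group, Visit 1 total and propensity quintile. Note that it targets a different estimand if baselines differ; its answer can depart from the primary by about (1 − r) times any baseline gap left after adjustment.
4. In section 6.4, label 15.0 and 6.8 points as unadjusted change-score figures. If adjusted values are wanted, 15.3 to 16.7 and 6.8 to 7.5 points are indicative, under the stated assumption that the r = 0.5 precision loss carries over.

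No new data are needed: Visit 1 scores and quintiles are already planned. The costs are a simulated 1.5 to 11% increase in the standard error and two analyses to interpret together. The changes should be documented before outcome data are examined.
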